4.1.4 Safety Analysis Set (Infants)

The safety analysis set of infants (SAFI) will be the same as the FASI.

4.1.5 Antibody Immune Response Analysis Set (Infants)

The antibody immune response analysis set of infants (AIRI) will include all infants in the SAFI for whom any serum titers of antibody immune response to vaccinations are available. This analysis set will be used to analyze humoral immune responses to common childhood immunizations.

4.1.6 Pharmacokinetic-Analysis Set (Infants)

The pharmacokinetic analysis set of infants (PASI) will include all infants in the FASI with a serum sample and umbilical cord (all available data) to allow measurement of ocrelizumab concentration. This analysis set will be used to estimate the serum concentration of ocrelizumab in the infant due to ocrelizumab transfer from the mother to the infant via the umbilical cord blood at birth.

4.2 ANALYSIS OF STUDY CONDUCT

Patient disposition information will be summarized separately for the mother and infant as: the reason and number of screen failures (women only), the number enrolled, in the respective full analysis set (FAS) population, in the respective safety analysis set (SAF) population, completed each study period, discontinued from each study period and the reasons for discontinuation.

Major protocol deviations, including deviations of inclusion/exclusion criteria, will also be summarized and listed.

Mothers and infants enrolled but excluded from the respective FAS will be listed.

4.3 DEMOGRAPHIC AND BASELINE CHARACTERISTICS

4.3.1 Women

The following demographic, MS history, baseline disease characteristics of women will be summarized and listed for the FASW, unless otherwise stated:

Demographic

- Age (years) as continuous and categorical (18–29, 30–40, >40)
- Self-reported race and ethnicity
- Education level
- Height (cm), weight (kg), and Body Mass Index (BMI: kg/m²)

- Smoking history (never, former)
- If previous smoker, time (years) since last use
- Alcohol use history (never, former)
- If previous user of alcohol, time (years) since last use

Multiple Sclerosis History

- Type of MS (relapsing-remitting multiple sclerosis [RRMS], secondary progressive multiple sclerosis [SPMS], primary progressive multiple sclerosis [PPMS], CIS)
- Duration (years) since onset of MS symptoms and its category (≤3 years, >3 to ≤5 years, >5 years to ≤10 years, >10 years to ≤15 years, >15 years)
- Duration (years) since MS diagnosis and its category (≤3 years, >3 to ≤5 years, >5 years to ≤10 years, >10 years to ≤15 years, >15 years)
- Expanded disability status scale (EDSS)
 - Change in EDSS score from last pre-baseline measurement (up to 1 year before LMP) to baseline
 - EDSS score:
 - Most recent prior to LMP: continuous and categorical (<2 vs \geq 2)
 - Last score prior to enrollment : continuous and categorical (<2 vs \geq 2)
- Relapses
 - Women with relapses up to 1 year prior to the LMP (yes, no)
 - Duration (Weeks) of most recent relapse and enrollment and its category (≤4 weeks, >4 and ≤8 weeks, >8 and ≤12 weeks, >12 and ≤16 weeks, >16 weeks)
 - Duration (months) between last onset of MS relapse up to one year prior to LMP and LMP and its category (≤6 months, >6 and ≤12 months)
 - Duration (months) between last onset of MS relapse after LMP prior to enrollment and enrollment and its category (≤6 months, >6 months)

If the date of the relapse is completely missing the relapse will be excluded from the analysis as appropriate. If only the year is available, it will be imputed to the first day of the year. If the day is missing, it will be imputed to the first day of the month.

Prior DMT Use

- Number of DMTs used prior to screening (1, 2, 3 and >3)
- Type of DMTs used prior to screening
- Number of women by the most recent DMT
- Reason for discontinuing most recent DMT

Ocrelizumab—F. Hoffmann-La Roche Ltd

Statistical Analysis Plan MN42988

- Duration of the most recent DMT as continuous and categorical (≤6 months, >6 and ≤12 months, >12 and ≤24 months, >24 months)
- Time (months) from last DMT to first ocrelizumab infusion before enrollment
- Time (months) from last DMT to LMP

Prior Ocrelizumab Use

- Number and percentage of women received ocrelizumab in 3-month interval of before/during pregnancy (3-6 prior LMP, 0-3 month prior to LMP, 1st trimester)
- Time (months) between last ocrelizumab before LMP and LMP
- Time (months) between LMP and last ocrelizumab after LMP
- Received ocrelizumab after LMP (yes, no)
- Duration (months) of ocrelizumab therapy prior to enrolment
- Duration of ocrelizumab therapy prior to enrolment (≤6 months, >6 and ≤12 months, >12 and ≤24 months, >24 months)

Prior Medications

Prior medication (defined as treatment ended before LMP) and concurrent medications (defined as treatment started on or after the LMP) will be summarized, by frequency tables according to the Anatomic Therapeutic Chemical (ATC) classification system using the WHO Drug dictionary.

Baseline Disease Characteristics

- Baseline EDSS continuous and categorical (<2.5 vs ≥2.5)
- Baseline EDSS distribution: count and percent of patients corresponding to each observed score of EDSS at baseline
- Presence of any clinically significant abnormalities from the neurological examination (Yes, No)
- Type of neurological abnormality (disability progression independent of relapse, MS relapse, signs or symptoms suggestive of Progressive Multifocal Leukoencephalopathy, Other)

Obstetric and Gynecological History

- History of previous pregnancies (Yes/No)
- Number of previous pregnancies (1, 2, 3, 4, >4)
- Previous pregnancy outcome (Full term live birth, preterm live birth, spontaneous abortion, still birth, therapeutic abortion, elective abortion, ectopic pregnancy, unknown)

- Gestational Age (Weeks) as continuous and categorical (<23, 23-27, 28-32, 33-36, ≥37)
- History of adverse pregnancy outcomes (Yes/No)
- History of obstetrical complications during previous pregnancies (Yes/No)
- Type of obstetrical complication during previous pregnancies
- Reason for termination (if terminated)

Medical History

Medical history of the women will be summarized in SAFW by System Organ Class (SOC) and Preferred Term (PT). For each previous and concurrent medical history recorded medical history (MH), the term entered by the investigator describing the event (the "reported term") will be assigned a standardized term (the "Preferred Term" [PT]) and assigned to a superclass term (the "System Organ Class" [SOC]) on the basis of the Medical Dictionary for Regulatory Activities (MedDRA) World Health Organization (WHO) dictionary of terms.

Previous and concurrent medical history will be also listed.

Vaccination History

Severe acute respiratory syndrome coronavirus 2 (SARS-CoV-2) vaccination history will be summarized in the SAFW overall and split by the period prior to infant's birth and before/after LMP and after infant's birth. Non-SARS-CoV-2 vaccination history will be summarized by pathogen (Appendix 5) in SAFW overall and split by the period prior to infant's birth and before/after LMP and after infant's birth. Where time period can't be determined due to completely or partially missing date, it will be imputed to before infant's birth.

SARS-CoV-2 vaccination history will also be listed in the SAFW, including the following:

- Manufacturer name (first, second and, if applicable, third dose and any booster dose[s]) (Pfizer/Biontech coronavirus disease of 2019 [COVID -19] vaccine, Moderna COVID -19 vaccine, Astra Zeneca COVID -19 vaccine, Johnson and Johnson Covid-19 vaccine, Other)
 - Type of vaccine for each dose (mRNA vaccine, Viral Vector Vaccine, Inactivated Vaccine, Other)
 - Timepoint of last COVID-19 vaccination prior to LMP (>6months before LMP, 3-6 months before LMP, <3 months before LMP, 1st trimester, 2nd trimester, 3rd trimester, ≤6 months postpartum, >6 months postpartum).

Other Vaccinations history (vaccines other than SARS-CoV-2) will also be listed in the SAFW.

4.3.2 Infants

The following baseline characteristics of infants will be summarized and listed in the FASI:

Characteristics at Birth

- Details of birth (vaginal delivery, vaginal delivery forceps/vacuum instrumental, cesarean scheduled, cesarean emergency)
- Gestational age (weeks)
- Gestational age category (pre-term, full-term)
- Sex (male, female)
- Weight (kg)
- Length (cm)
- Head circumference (cm)
- Apgar score 1 minute
- Apgar score 5 minute
- Apgar score 10 minute
- Congenital anomalies

The listing of characteristics at birth will also include congenital anomalies.

Infant feeding

- Feeding status (Breast Milk, Infant Formula, Partial Breast Milk/infant formula, Other) at Months 2, 4, 6, 9, and 12 by no switch of DMT, switch to another DMT regardless of timing and overall.
- Number of weeks exclusively breastfed by visit.

4.4 PRIMARY ENDPOINT ANALYSIS

The primary analysis will be performed after the last blood draw at Week 6 of life to examine B cell levels in infants. The full analysis, including the analysis of growth velocity of the infants in the first year, will be conducted at the end of the study.

4.4.1 Primary Endpoint

The primary endpoint is binary, defined as the proportion in infants with B cell levels (CD19+ cells, absolute counts) below the LN), measured at Week 6 of life (Yes/No).

The primary estimand is defined as follows:

- Population: Infants exposed to commercial ocrelizumab up to 6 months before the woman's LMP or during the first trimester (up to gestational Week 13) of pregnancy and not exposed after the first trimester (FASI)
- Variable: Binary endpoint, based on whether the B cell level is below the age adjusted LLN.

- Treatment: Commercial ocrelizumab (potential exposure during pregnancy).
- Intercurrent events:
 - Withdrawal from the study prior to infant's Week 6 visit missing data will not be imputed
 - Interrupted pregnancy (elective/therapeutic abortion or stillbirth) missing data will not be imputed
 - Fetal complications, or other issues, that render the sample not suitable for measurement of B cell levels at week 6 of life. – missing data will not be imputed
 - Breastfeeding before sample at week 6 is taken:
 - \circ $\,$ No DMT postpartum whilst breastfeeding: B cell will be included
 - Received any DMT postpartum whilst breastfeeding: B cell will be excluded since sample will not be collected.
 - Resume OCR postpartum whilst breastfeeding: B cell will be included.
 - Infants that were born pre-term and whose interval of assessment was not adjusted (i.e. a baby was born at week 35, the blood sample needs to be taken at week 8 (±14 days), gestational weeks that would sum up to a full term baby): B cell will be included.
- Population-level summary: Proportion of infants with B cell below LLN and the two-sided 95% CI will be reported; no formal statistical testing will be done.

B-cell reference ranges by week of life (absolute and percentage counts) are defined by Borriello et al. 2022 (Appendix 4). B cell data being confounded with illness will be determined by clinical team in a blinded manner before conducting the primary analysis.

4.4.2 Analytical Approach for Primary Endpoint

The proportion of infants with B cell levels at Week 6 of life below the LLN will be analyzed using descriptive statistics. The event rate and corresponding Clopper Pearson 95% CI will be presented. A corresponding listing will be presented for B cell levels (absolute count), including whether any intercurrent events (ICEs) led to exclusion of infant data from the analysis.

4.4.3 Handling of Missing Data

No data will be imputed unless otherwise stated. Every effort will be made to ensure all samples with all supporting information are collected for B cell measurement.

4.4.4 Sensitivity Analysis for Primary Endpoint

The following sensitivity analyses may be performed on the primary endpoint if more than 20% of infants are impacted. Infant with any of the following condition will be considered as being impacted:

- infants blood samples collected outside the Week 6±7 days visit window.
- gestational age is less than 37 weeks, but interval of assessment is not adjusted.
- resume OCR postpartum whilst breastfeeding before sample at Week 6 is taken.

A sensitivity analysis may be conducted substituting any B Cell values with missing data.

4.4.5 Subgroup Analyses for Primary Endpoint

To assess the impact of fetal exposure during pregnancy, a subgroup analysis will be performed of infants based on maternal OCR exposure prior to the study as list below:

- in 3-month interval of before/during pregnancy (3-6 months before the LMP, <3 months before the LMP, during the first trimester [up to gestational Week 13]
- ≥3 months before the LMP vs <3 months before the LMP and/or during pregnancy.

The analysis will be presented in the same way as for the primary endpoint

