3.3.2 Rationale for Patient Population

As the aim of this study is to evaluate placental transfer of ocrelizumab and the corresponding pharmacodynamic effects, it will be conducted in women with CIS or MS (in line with the locally approved indications) aged 18–40 years who received ocrelizumab any time up to 6 months before the LMP or during the first trimester of pregnancy (up to gestational Week 13).

Based on the average terminal half-life of 26 days (Ocrelizumab USPI), ocrelizumab is expected to be eliminated from the body by approximately 4.5 months, with the longest terminal half-life recorded as 53 days in one woman. Considering the interpatient variability and the fact that ocrelizumab, as a fully humanized IgG1, is not expected to cross the placenta in the first trimester (Palmeira et al. 2012; Simister 2003), it is assumed that a potential fetal exposure is unlikely in women whose last ocrelizumab infusion was earlier than 3 months before conception. Therefore, women who received ocrelizumab 3–6 months before conception will represent the non-exposed group. Women who received ocrelizumab up to 3 months before conception or during the first trimester of pregnancy will represent groups with potential fetal exposure. Women who received ocrelizumab after the first trimester will be excluded since placental transfer of IgG is known to be significant after the first trimester (Palmeira et al. 2012; Simister 2003).

The maximum age is set at 40 years since only a minority of pregnancies occur after this age (e.g., only around 3% of births of first children in the EU in 2017 were to women aged 40 and over [Eurostat 2019] and in the United States, the birth rate in 2018 was the lowest for the 40-44 age group [CDC2019]). Additionally, advanced maternal age is associated with higher rates of maternal and fetal complications (Bouzaglou et al. 2020). Fetal complications, if they occur, may prevent the collection of the required sample or confound the interpretation of B-cell levels in the infants (the primary endpoint of the study).

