6.4.3 Exploratory Endpoints

The exploratory endpoints listed in Section 2 will be summarized descriptively. Full details of the derivations and analyses of exploratory endpoints will be provided in the SAP.

6.4.4 Subgroup Analyses

The subgroup of infants with potential fetal exposure (infants of mothers with ocrelizumab exposure 0-3 months before the LMP or first trimester exposure) will be analyzed.

The following subgroups, based on timing of ocrelizumab exposure relative to the LMP, may be analyzed, depending on how many women/infants are enrolled in each group: (1) exposure to ocrelizumab 3–6 months prior to the LMP; (2) exposure to ocrelizumab in the 3 months prior to the LMP; (3) exposure to ocrelizumab during the first trimester of pregnancy (up to gestational Week 13).

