4. STATISTICAL METHODS

The analysis of this open-label study will be primarily based on descriptive statistical methods. Unless otherwise specified, no statistical tests are planned. Corresponding 95% Cls will be presented as appropriate.

For continuous variables, descriptive statistics (e.g., number of patients [n], mean, standard deviation [SD], median, 25th and 75th percentiles, minimum, maximum) will be calculated and summarized.

For categorical variables, the number and percentage in each category will be displayed.

The analyses outlined in this Statistical Analysis Plan (SAP) supersede those specified in the protocol.

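### SAP 4.4.5 sets out to assess the impact of fetal exposure and names a two-group split, but plans no estimate or interval for the difference between the two groups

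*SAP*

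**What the plan says.** SAP 4.4.5 opens with its purpose: "To assess the impact of fetal exposure during pregnancy, a subgroup analysis will be performed of infants based on maternal OCR exposure". It then lists two groupings by timing of the mother's last dose. The first has three levels: 3–6 months before the LMP, under 3 months before the LMP, and first trimester. The second has two: "≥3 months before the LMP vs <3 months before the LMP and/or during pregnancy".

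The method is one sentence: "The analysis will be presented in the same way as for the primary endpoint". That presentation is set out in SAP 4.4.2: "The event rate and corresponding Clopper Pearson 95% CI will be presented", with a listing of the B-cell values. The estimand in SAP 4.4.1 adds: "Proportion of infants with B cell below LLN and the two-sided 95% CI will be reported; no formal statistical testing will be done". SAP section 4 says the same of the whole plan: "Unless otherwise specified, no statistical tests are planned".

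The protocol provides a comparator. Section 3.3.2 states: "Therefore, women who received ocrelizumab 3–6 months before conception will represent the non-exposed group". On priority, Protocol 6.4.4 commits to analysing the pooled potentially exposed subgroup, whereas the three timing groups "may be analyzed, depending on how many women/infants are enrolled in each group". SAP 2.2 also singles out the pooled subgroup for further investigation.

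For this endpoint, neither the SAP nor Protocol 6.4.1 or 6.4.4 gives a risk difference, a ratio, or an interval for either.

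**The concern.** An impact of exposure on a proportion is a difference between groups. The plan has the aim, a designated non-exposed group and a two-group split, but it stops at one interval per group. The reader has to compare two one-sample exact intervals by eye. That is a much stricter yardstick than an interval for the difference, because two 95% intervals can overlap while the 95% interval for the difference excludes zero.

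The primary estimand pools exposed and non-exposed infants, so for the primary endpoint SAP 4.4.5 is the only place where the exposure question is addressed. What is at stake is that a sizeable excess of low B-cell counts in potentially exposed infants could be taken as unremarkable because the two intervals overlap.

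**Working it through.** **Inputs.** About 33 women and 10% dropout (SAP 2.2): 33 × 0.9 = 29.7, so about 30 infants. Two-sided 95% intervals (SAP 4.4.1). Non-exposed event rate of 2.5%, because SAP Appendix 4 defines the LLN as the 2.5th percentile. The split between groups is not given; 15/15 is an assumption, and other splits are shown below.

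**The plan's own figure.** The documents give no figure for the comparison. The nearest is the upper bound of 0.114 for 0/30 in SAP 2.2. The Wilson limit reproduces it: z²/(n + z²) = 3.8415/33.8415 = 0.1135. The exact two-sided limit is 1 − 0.025^(1/30) = 0.116.

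**Planned output for 0/15 vs 5/15.** This places all 5 events of the last row of SAP Table 1 in the exposed group.
- 0/15: upper limit 1 − 0.025^(1/15) = 0.218, so 0 to 0.218.
- 5/15: Clopper-Pearson 0.118 to 0.616.
- Since 0.118 < 0.218, the intervals overlap.

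**Difference for the same data (Newcombe).**
- Wilson limits for 0/15: 0 and 3.8415/18.8415 = 0.204. For 5/15: 0.152 and 0.583.
- Difference: 5/15 − 0 = 0.333.
- Lower limit: 0.333 − √[(0.333 − 0.152)² + 0.204²] = 0.060.
- Upper limit: 0.333 + √[(0.583 − 0.333)² + 0²] = 0.583.
- Result: 33%, 95% CI 6% to 58%. Fisher's exact p, as a yardstick only, is 0.042.

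**How far the overlap goes.** At 7/15 the Clopper-Pearson interval is 0.213 to 0.734, which still overlaps 0 to 0.218, by 0.005. At 8/15 the lower limit is 0.266 and the intervals separate. For 7/15 vs 0/15 the difference is 46.7% (Newcombe 16.8% to 69.9%; Miettinen-Nurminen 21.5% to 70.2%).

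**Other splits.** Largest exposed count whose interval still overlaps that of a non-exposed group with zero events:

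| Non-exposed / exposed | Largest overlapping count | Difference (Newcombe 95% CI) |
|---|---|---|
| 5 / 25 | 18/25 | 72.0% (24.3% to 85.7%) |
| 8 / 22 | 13/22 | 59.1% (20.8% to 76.7%) |
| 10 / 20 | 10/20 | 50.0% (15.8% to 70.1%) |
| 15 / 15 | 7/15 | 46.7% (16.8% to 69.9%) |
| 20 / 10 | 4/10 | 40.0% (11.8% to 68.7%) |
| 22 / 8 | 3/8 | 37.5% (9.4% to 69.4%) |
| 25 / 5 | 2/5 | 40.0% (8.8% to 76.9%) |

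In every row the planned intervals overlap and the difference interval excludes zero.

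**How often it matters.** Exact enumeration: sum Bin(x; n₁, p₁) × Bin(y; n₀, 0.025) over all outcomes (x, y) that meet the criterion, where subscript 1 is the exposed group.

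| Exposed / non-exposed | True rates | Planned intervals separate | Newcombe CI excludes 0 |
|---|---|---|---|
| 15 / 15 | 16.7% vs 2.5% | under 1% | 17% |
| 15 / 15 | 20% vs 2.5% | under 1% | 26% |
| 15 / 15 | 40% vs 2.5% | 17% | 80% |
| 15 / 15 | 50% vs 2.5% | 42% | 93% |
| 20 / 10 | 40% vs 2.5% | 10% | 63% |

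With 15/15, true rates of 40% and 2.5% imply (40 + 2.5)/2 = 21.25% overall, above the largest rate in Table 1 (16.7%).

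**The case against.** The strongest reply is that the study is declared descriptive. No tests are planned, the primary objective concerns a single cohort, no group sizes are set, and the groups are not randomized. Neither document makes overlap of intervals a decision rule, and anyone can compute the difference from the reported counts. Protocol 3.3.2 also defines non-exposed relative to conception, whereas SAP 4.4.5 groups by LMP, so the comparator is not cleanly carried over.

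Much of this stands. The absence of a p-value is not a fault, and misreading overlap would be the reader's error. The benefit is also uneven. At exposed rates of 16.7% to 20%, the difference interval would include zero about three times in four or more. Newcombe is on the liberal side: at 4/15 vs 0/15 it excludes zero (0.9% to 52.0%) while Fisher's p is 0.0996. At 40% vs 2.5%, Fisher's p falls below 0.05 with probability 64%, against 80% for the Newcombe interval.

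What does not stand is that a descriptive design rules out the estimate. A difference with an interval is estimation, and SAP section 4 provides for 95% intervals as appropriate. Small groups are a reason to show how wide the interval is.

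A reader might infer more than the documents support:
- That no contrast is named. The second bullet of SAP 4.4.5 names one; only the effect measure is missing.
- That the SAP abandons the protocol's priority for the pooled exposed group. SAP 4.4.5 itself ranks neither grouping, but SAP 2.2 still singles out that group.
- That a comparison could be picked from several after the results are seen. The SAP plans no set of pairwise contrasts and commits to presenting both groupings.

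**Conclusion.** The point holds as a gap between aim and output. SAP 4.4.5 asks about the impact of exposure and names the groups, but yields no estimate of the difference and no interval for it. The gap is material if the effect is large and modest if it is not: at 15/15, 80% against 17% when true rates are 40% vs 2.5%, but only about 17% for the difference interval at 16.7% vs 2.5%. These figures rest on 30 evaluable infants, the assumed split, and a 2.5% rate in non-exposed infants taken from the definition of the LLN. The overlap pattern itself holds for every split checked, from 5/25 to 25/5. The documents do not support reading the plan as one that would declare no effect because intervals overlap. The change is worth making because it answers the stated aim at almost no cost.

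**What to change.** In SAP 4.4.5, for the two-group split already listed, add the difference in the proportion of infants below the LLN (under 3 months before the LMP and/or during pregnancy, minus 3 months or more before the LMP). Give it a two-sided 95% Newcombe or Miettinen-Nurminen interval, with the method fixed in advance, beside the two Clopper-Pearson proportions. Label it descriptive and non-confirmatory. State that this pooled split is the main exposure comparison and that the three-way split is supportive, which agrees with SAP 2.2 and Protocol 6.4.4.

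The cost is two sentences and one row in an existing table, with no new data and no test. The small downside is that a difference from a non-randomized comparison with no planned group sizes may be over-read; the label and the width of the interval limit that.
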